In summary, (i) few studies have measured DD directly and have identified the explicit sources of DD among T1D adults; (ii) the content of interventions have often been focused solely on education and behavior change, with DD change often considered a secondary outcome; (iii) no studies have used an integrated framework that addressed DD-related emotions and cognitions, and none have addressed how they directly influenced diabetes management and glycemic control; and (iv) very few studies included T1D adults with high baseline DD and HbA1C, making it difficult to identify interventions that reduce both DD and HbA1C and determine their relationships. This study builds upon this literature by addressing each of these issues directly.

Recruitment. Adults with T1D will be recruited by partnering with academic clinics' research registries and community-based organizations. Partnering organizations will send e-mails and/or social media posts to their members. Patients who are eligible and interested during telephone screening will be emailed a link to a secure electronic consent and online baseline survey, with a copy of the consent emailed for their records. Patients who are eligible following completion will be sent a pre-paid slip to

collect HbA1C at a local laboratory to confirm HbA1C eligibility. HbA1C collection will be 5.0ml of whole

Follow up will occur at 3, 6, and 12 months following Group Meeting 1, and procedures will be the same for each group. Participants will be emailed a link to a secure online follow up survey, plus a pre-paid slip to collect HbA1C at a local laboratory. HbA1C collection will be 5.0ml of whole blood.

Interventions:

1. **StreamLine** (management strategy)
2. **TunedIn** (DD-targeted strategy)
3. **FixIt** (unified strategy)

Each of the 3 study arms will selectively include: (a) a group workshop (8-10 participants), (b) real-time online video group meetings and (c) individual phone/video calls or face-to-face meetings with the interventionist (summarized in Table 1).

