StreamLine (management strategy) is an education/disease management program that focuses directly on identifying and resolving specific BG problems; no DD-related component is included. StreamLine focuses on systematic methods to identify and resolve specific BG problems, primarily through changes in carbohydrate consumption, and basal and bolus insulin use. Participants will attend a brief, 4-hour didactic non-interactive meeting with a certified diabetes educator (CDE) and, using standardized BG data, will learn how to employ a 5-point BG management system to identify and resolve BG problems (e.g., excursions, lows) that have the greatest HbA1C or hypoglycemia impacts: (1) utilizing BG pattern data, and (2) examining basal insulin rates, (3) frequency of binging, (4) timing of bolusing, and (5) amount of insulin bolused. Participants will leave the session to record 3 days of structured, seven-point glucose testing, either through continuous glucose monitoring (CGM) or finger stick (participants' own devices; these will not be provided by the study) during the following week. They will then meet individually (face to face, phone/video, 30 minutes) with their CDE to review their BG data, identify a specific BG problem, and adjust their current management to resolve the problem, using the 5-point program. Four additional individual participant/facilitator meetings (face to face, phone/video, 30 minutes) will occur at approximately two to three-week intervals to best support individualized and participant-tailored management-change efforts. If indicated by the facilitator and/or clinical supervisors, based on participant need, an additional one to two individual contacts may be scheduled during the intervention period.

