TunedIn (DD-targeted strategy) utilizes exercises and scenarios of ER-based strategies that were effective in reducing DD in the OnTrack arm of T1REDEEM6, now greatly expanded in number and focused in intensity to be more comprehensive and inclusive to help participants observe how what they feel affects what they do regarding disease management. Taking advantage of the power of facilitated group interaction in reducing DD, participants in TunedIn will attend 2 highly interactive group workshops (6 hours followed by 2 hours), facilitated by a psychologist or social worker experienced in diabetes. Each will identify and discuss common emotional responses related to BG management (e.g., over-reacting, avoiding, lack of mindfulness). Between the two workshops (2 weeks), participants will

blood. For those patients who are unable to go to a local laboratory, we will provide a HbA1C home test kit mailed to their home address for their convenience and comfort. After blood sample is provided by patient (instructions are provided in each test kit), they will mail the kit back to the lab to be analyzed. Randomization of eligible participants will occur after baseline assessments. Sequential ID numbers will be generated and randomly assigned to the 3 study groups. Each participant will receive the next ID number, contained in a REDCap database. Block randomization stratified by clinical recruitment site will be used to ensure equivalent distributions in the three intervention study arms across sites. complete a "feeling log," a tool commonly used in ER-based programs, in which participants document.

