FixIt (unified strategy) seamlessly integrates StreamLine and TunedIn. It makes use of the same highly interactive group discussion around affect management using ER techniques and affect logs used in TunedIn with the same 5-point glycemic-management program used in StreamLine. Thus, interconnected feelings and expectations are highlighted as problematic BG patterns are identified. To ensure the delivery of a balanced, integrated approach, FixIt will be co-facilitated by a psychologist/social worker experienced in diabetes (as in FixIt) and a CDE (as in StreamLine). Participants will attend 2 group workshops (6 hours followed by 4 hours), separated by 2 weeks. Between the 2 workshops, participants will record their BG data for 3 days and keep a parallel “affect log” to provide context. They will then meet face to face or through phone/video for 30 minutes with one of their 2 group interventionists to review the collected data and begin the process of identifying a specific glycemic problem, along with an action plan to address it. Full discussion of DD-related aspects of the plan will also be included to both enhance mindfulness and identify typical ER strategies that may reduce DD and ease problem resolution. At the second group session, these plans will be shared to shape the plan to make it more personally actionable. Participants will be further supported by: 3 online video group meetings (60 minutes, monthly) utilizing facilitated group discussion to review specific plans addressing behavioral and affective management for each participant, and 3 additional individual participant/facilitator meetings (face to face or phone/video, 30 minutes) to review BG data and the contextual and DD barriers to change. This strategy, therefore, combines the primary intervention modalities of StreamLine and TunedIn.

Measures

Telephone screening questions will document: age, years with T1D, age at diagnosis, insulin treatment (multiple-dose injection [MDI], CGM, insulin pump), co-morbidities and diabetes-related complications, and English language skills (attached). Self-reported surveys completed electronically will include the following measures:

- The **number of hypoglycemic episodes** will be assessed, including: frequency of symptomatic hypoglycemia (BG < 70 Mg/dL) in the past week and episodes of hypoglycemia in the past 6 months (or since last follow-up) requiring the assistance of another person or medication intervention (2 items)⁸².

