Data Analysis. Descriptive statistics will be computed for baseline characteristics, initially testing for differences between: (1) intervention arms and (2) patient dropouts vs. non-dropouts. Patient-level demographic and disease status covariates will be screened in bivariate analyses and included in multivariate analysis if they are related to the outcome at $p < .20$, significantly differ between treatment arms, or are associated with dropout. Correlations among variables within each area of secondary outcomes and moderators (see measures above) will be examined, and redundant measures will be combined or eliminated to avoid multicollinearity. In the event normality assumptions are not met, we will use transformations to normalize distributions, ordinal or Poisson regression where appropriate, and/or the appropriate link function (e.g., logit link for dichotomized measures)⁹⁵⁻⁹⁷. We will examine change in outcomes across groups will be evaluated by ANCOVA. In these models, the follow-up value is specified as the outcome, the baseline value as the covariate, and treatment group was a fixed effect. When the treatment group effect was statistically significant ($p < 0.05$), Helmert contrasts will be used to determine differences among the three groups. Missing values will be imputed with NORM software (version 2.0; The Methodology Center, Penn State, University Park, PA) (23,24) using multiple-imputation procedures to create a stable, complete data set. Parallel analyses will be performed with raw and imputed data sets. Hypothesis tests will be 2-sided with alpha set at .05. Goodness-of-fit tests and model-fitting diagnostics will be used to assess for influential points, outliers, over-dispersion, and heteroscedasticity, and to evaluate alternative model specifications.¹⁴³

Intervention implementation costs on a per-participant basis, and training costs on a per-facilitator basis, will be calculated using activity-based costing methods. Costs for staff time will be assigned based on the prevailing national wage rate as reported in the Bureau of Labor Statistics' Occupational Outlook Handbook in the final year of intervention implementation⁹². All other costs will be adjusted for inflation

to constant U.S. dollars for the final year of implementation using the Bureau of Labor Statistics'

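### TunedIn and FixIt are delivered in interactive groups of 8-10, but the planned ANCOVA and Helmert contrasts have no intervention-group term, so standard errors are too small if outcomes correlate within groups

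*Combined protocol and SAP*

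**What the plan says.** The Interventions section describes arms that draw selectively on "a) a group workshop (8-10 participants), (b) real-time online video group meetings" and individual contacts. The three arms differ in how far they rely on the group:

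- TunedIn: "Taking advantage of the power of facilitated group interaction in reducing DD, participants in TunedIn will attend 2 highly interactive group workshops".
- FixIt: "It makes use of the same highly interactive group discussion around affect management using ER techniques and affect logs used in TunedIn". It has two workshops, three online group meetings and some individual meetings. On the participants' plans for a glycemic problem: "At the second group session, these plans will be shared to shape the plan to make it more personally actionable".
- StreamLine: a "4-hour didactic non-interactive meeting with a certified diabetes educator (CDE", followed by individual contacts.

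The Data Analysis section specifies an ANCOVA for each outcome: "the follow-up value is specified as the outcome, the baseline value as the covariate, and treatment group was a fixed effect". Patient-level covariates may be added after screening. If the arm effect is significant at 0.05, "Helmert contrasts will be used to determine differences among the three groups". On model checking: "Goodness-of-fit tests and model-fitting diagnostics will be used to assess for influential points, outliers, over-dispersion, and heteroscedasticity"; the sentence ends by allowing other model forms to be evaluated.

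The sample size paragraph uses t tests on change from baseline, 90 per group and 20% attrition. The Research Design section plans 118 per arm. Randomization is of individuals, in blocks stratified by recruitment site. No intervention-group term, cluster-robust variance or ICC appears in the analysis or sample size text.

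**The concern.** The ANCOVA treats all participants as independent. In TunedIn and FixIt, people in one group share its composition, its discussion and its facilitators, so their outcomes may be correlated.

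For diabetes distress, a primary outcome, the protocol itself supplies the mechanism: it credits group interaction with reducing distress, and FixIt uses the same discussion. For HbA1c, the other primary outcome, the support is less direct. It is clearest in FixIt, where plans are shared and reshaped in the group.

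With positive within-group correlation, the model understates the variance of arm means in the two grouped arms. The comparison most exposed is FixIt vs TunedIn, because both arms are grouped. It is a named part of Hypothesis 1, and the error favours false claims of a difference.

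**Working it through.** **Inputs from the documents.** Two-sided alpha is 0.05. Groups hold 8-10 people (9 used). With 20% attrition, 9 × 0.8 = 7.2 are analysed per group. Groups per arm: 90/9 = 10, or 118/9 ≈ 13.

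**Assumptions.** ICC from 0.01 to 0.10, on the baseline-adjusted outcome; StreamLine participants independent; baseline correlation 0.5 in the main simulations.

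**The plan's own figure.** 2 × (1.960 + 0.842)² / 0.47² = 71.1, rounded up to 72 analysed per arm, and 72/0.8 = 90. The stated 90 is therefore reproduced by a calculation for independent participants at 80% power. That power is inferred, since the documents state none.

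**Each contrast taken alone, without the overall-test condition.** The design effect is DE = 1 + (7.2 − 1) × ICC. The ratio of true to assumed variance is:

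- FixIt vs TunedIn: DE
- StreamLine vs the mean of the other two: (1 + DE/2)/1.5
- FixIt vs the mean of the other two: (DE + (1 + DE)/4)/1.5
- TunedIn vs StreamLine: (1 + DE)/2

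Actual error = 2 × (1 − Φ(1.96/√ratio)). Example, FixIt vs TunedIn at ICC 0.05: DE = 1.310, 1.96/√1.310 = 1.712, error 8.7%.

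| ICC | DE | FixIt vs TunedIn | StreamLine vs mean | FixIt vs mean | TunedIn vs StreamLine |
|---|---|---|---|---|---|
| 0.01 | 1.062 | 5.7% | 5.2% | 5.6% | 5.4% |
| 0.02 | 1.124 | 6.4% | 5.5% | 6.2% | 5.7% |
| 0.05 | 1.310 | 8.7% | 6.2% | 8.1% | 6.8% |
| 0.10 | 1.620 | 12.4% | 7.4% | 11.1% | 8.7% |

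The standard error for FixIt vs TunedIn is too small by 3%, 6%, 13% and 21% in these four rows. At ICC 0.05, taking 6.4 or 8.0 analysed per group (groups of 8 or 10) changes its error rate to 8.2% or 9.2%. The plan does not state the Helmert order, so both possible pairs of contrasts are shown.

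**The planned sequence, by simulation.** Three-arm ANCOVA, 10 groups of 7 in TunedIn and FixIt, 70 independent participants in StreamLine, 40,000-60,000 trials per setting:

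| Rejection rate at ICC | 0 | 0.02 | 0.05 | 0.10 |
|---|---|---|---|---|
| Overall test, arms equal | 5.0% | 6.1% | 8.1% | 11.7% |
| FixIt vs TunedIn after a significant overall test, arms equal | 2.4% | 3.4% | 4.8% | 7.5% |
| The same, StreamLine shifted by 0.5 SD | 5.0% | 6.4% | 8.6% | 12.2% |
| Overall test, only FixIt clustered | 4.9% | 5.6% | 6.5% | 8.3% |
| Overall test, 13 groups per grouped arm | 5.2% | 6.2% | 8.4% | 11.7% |

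Independent repeats of the first three rows agreed within 0.5 percentage points. At ICC 0.01 the overall test rejects 5.6%. The row with only FixIt clustered is a cautious case for HbA1c. The last row shows that enrolling more participants in groups of the same size does not remove the inflation.

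With all arms equal and the overall-test condition applied, a further simulation (20,000 runs, no baseline covariate) gave, at ICC 0.02 and 0.05: StreamLine vs the mean 2.8% and 3.5%; FixIt vs the mean 3.4% and 4.5%; TunedIn vs StreamLine 2.9% and 3.8%. Across the ICC range up to 0.10, these contrasts stay at about 3-7%.

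**The case against.** **The ICC is unknown and may be negligible.** This stands as a limit on size. At 0.01 the effect is trivial. For HbA1c the mechanism is inferred, and FixIt also includes individual meetings. Hypothesis 1 concerns 12 months, nine months after the intervention ends, by when the correlation may have faded. A reader might take 8-12% as the expected error rate; the documents give no basis for that.

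**The overall test protects the contrasts.** This stands in part. A reader might infer that every Helmert contrast exceeds 5% whenever the ICC is positive. That is wrong: when all arms are equal, the requirement of a significant overall test holds the contrasts below 5% at ICC 0.02 and to about 5% or less at 0.05. But the overall test is itself inflated. It also gives FixIt vs TunedIn little protection once StreamLine differs, which is what Hypothesis 1 predicts.

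**The plan allows other model forms to be evaluated.** It does, but this commits to nothing on within-group dependence, and the listed diagnostics do not look for it.

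**Individuals are randomized, stratified by site.** True, but the grouping arises through treatment after randomization, and site strata do not capture it.

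**StreamLine may not be independent.** It opens with a shared meeting and has educators in common, and facilitators may be shared across groups. None of this is modelled here. Nor do the documents say that group membership stays fixed across sessions.

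**Is the stated d = 0.47 too favourable?** A reader might infer this too, but the documents do not support it. At 80% power, d = 0.47 needs 72 analysed. If 90 are analysed there is room for a design effect of 90/72 = 1.25; if 118 are enrolled, 118 × 0.8 = 94.4 leaves room for 94.4/72 = 1.31. ANCOVA may also be more efficient than the t test on change. At an assumed baseline correlation of 0.5 with 72 analysed, the detectable effect in change-SD units is 0.43, 0.47 and 0.52 at ICC 0.02, 0.05 and 0.10.

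**Conclusion.** The point holds in conditional form. The planned analysis has no means of reflecting correlation within intervention groups, and nothing else in the documents supplies one. If such correlation exists, standard errors and confidence intervals are too small in comparisons that involve TunedIn or FixIt.

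At assumed ICCs of 0.02, 0.05 and 0.10, the overall test runs at about 6%, 8% and 12%, and FixIt vs TunedIn at about 6%, 8.5% and 12% when StreamLine differs. When all arms are equal, FixIt vs TunedIn runs at about 3.4%, 5% and 7.7% after the overall test. The single-contrast rates of 5.5-12.4% at these ICCs apply only without that condition.

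These figures rest on the assumed ICC, about 7 analysed per group and an unclustered StreamLine arm. The support is firmer for diabetes distress than for HbA1c. This should be fixed, with medium confidence in how much it matters; no claim is made about the stated detectable effect.

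**What to change.** 1. Add a field for each participant's intervention group, defined as the assigned workshop group, so that later switching or mixed online sessions do not change it.
2. Prespecify a group-aware primary analysis for both the overall test and the contrasts. One option is a partially nested mixed model: baseline value and arm as fixed effects, a random group effect in TunedIn and FixIt (none, or a separate variance, for StreamLine), and Satterthwaite or Kenward-Roger degrees of freedom. Another is a Welch/Satterthwaite test on group means.
3. State the order of the Helmert contrasts.
4. Carry group membership into the multiple imputation.
5. When the model is changed, restate the detectable effect with its power, whether it rests on 90 or 118 and on enrolled or analysed participants, and an assumed ICC range.

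The group-mean test is the version that simulation showed to hold 4.9-5.3%. In a balanced two-arm check, the mixed model with its variance bounded at zero was somewhat conservative: about 3-4% at ICC 0, rising to about 4.7-4.9% at ICC 0.10.

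The cost is one data field, some analysis wording and some precision. If the ICC is truly zero, the mixed-model interval for FixIt vs TunedIn is on average about 9-12% wider with 10 groups per arm and 7-10% wider with 13. In some trials the loss is larger: 32% and 27% respectively at the 95th percentile.

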Behavioral Approaches to Reducing Diabetes Distress and Improving Glycemic Control (EMBARK)

NCT04016558

Study Protocol

8/10/2019

Behavioral Approaches to Reducing Diabetes Distress and Improving Glycemic Control (EMBARK)

Project Summary. Diabetes Distress (DD) is the personal, often hidden side of diabetes: it reflects the unique emotional burdens and strains that individuals with diabetes may experience as they struggle to keep blood glucose levels within range⁷. When high, DD can have a major, negative impact on disease management and glycemic control⁹. High DD is characterized by frustration, feeling overwhelmed, and feeling hopeless and discouraged by the unceasing demands of diabetes. DD is also linked to an individual's beliefs, expectations, current life situation, and personal and social resources¹⁰⁻²⁷.

There have been very few systematic interventions directly aimed at reducing DD among adults with T1D. Furthermore, systematic reviews^{4,5} conclude that, of the few interventions to date, most attempt to reduce DD only indirectly by providing diabetes education and/or enhancing disease management. These interventions, which have yielded only modest improvements in HbA1c, rarely address the powerful and persistent underlying affective experience of DD, and the direct impact of high DD on disease management.

The proposed study is a 3-arm, 12-month RCT to test the added value of a DD-targeted (TunedIn) intervention vs. a unified DD and management intervention (FixIt), relative to a traditional, educational/behavioral-management intervention (StreamLine). Each of the 3 arms will follow a separate, standardized protocol. All participants will receive 3 months of intervention with 9 months of subsequent follow-up (12 months total). We will examine models of disease-management behaviors as mediators of associations between DD and HbA1C, and explore the directions of longitudinal associations among DD, disease management and HbA1c.

Aims & Hypotheses:

Primary Specific Aim 1 Hypothesis 1. Improvement in primary (HbA1C, Diabetes Distress) and secondary (frequency of hypoglycemia, emotion regulation measures) outcomes from baseline to 12-month follow-up will be greater in TunedIn relative to StreamLine, and greater in FixIt relative to either TunedIn or StreamLine.

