Primary Specific Aim 2 Hypothesis 1 (Mediation Hypothesis). Decreases in DD will be significantly associated with decreases in HbA1C within each of the 3 intervention groups over 12 months. Associations between changes in DD and changes in glycemic control will be explained by changes in disease-management mediators (e.g., increased blousing) across all 3 intervention groups. In exploratory analyses, we will examine the direction of associations as presented in the conceptual models in Figure 3.

Secondary Specific Aim 1 Hypothesis 1 (Moderator Hypothesis). Differences in primary and secondary outcomes between FixIt and TunedIn will be qualified by: (a) patient characteristics (with stronger positive effects for younger age and patients with shorter T1D duration), (b) both baseline emotion regulation (ER) skills and level of DD (with stronger positive effects for patients with poorer ER skills and higher DD), and (c) baseline cognitive-processing constructs (with stronger positive effects for patients with lower problem-solving skills and diabetes knowledge).

Secondary Specific Aim 2 Hypothesis 1 (Cost-effectiveness). FixIt and TunedIn will be more cost-effective than StreamLine in terms of improvements in primary and secondary outcomes.

Research Design: This is a 3-arm, 12-month randomized comparison trial (baseline N=118 per arm) to test the added value of a DD-targeted intervention (TunedIn) vs. a unified DD and management intervention (FixIt), relative to a traditional, educational/behavioral-management intervention (StreamLine) to reduce diabetes distress and improve glycemic control in adults with type 1 diabetes. Additionally, the implementation costs and per-participant program costs will be calculated.

Each of the 3 arms will follow a separate, standardized protocol. All participants will receive 3 months of intervention with 9 months of follow-up (12 months total).

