Sample size and power estimates are based on two-sided $\alpha = 0.05$ and Student t tests on change from baseline to each follow-up point. Estimating a 20% attrition rate, a sample of 90 per group allows for detection of moderate effect sizes ($d = 0.47$ SD unit differences) equating to mean changes in DD of at least 0.36 and mean changes in HbA1c of at least 0.44%.

Inclusion criteria:

To be eligible to enter baseline assessment:

- Adult patients with T1D (confirmed by clinical history and/or anti-glutamic acid decarboxylase [GAD] antibody testing) on intensive insulin treatment;
- Diagnosis of T1D for at least 12 months that occurred at or below age 40;
- Age 19 years or older;
- Have a recent HbA1c of 7.2% or higher, or unable to recall most recent value;
- Not have started to use any new (to the participant) diabetes device (such as an insulin pump or continuous glucose monitor) in the past 6 months;
- Internet access through a computer or smart phone;
- Ability to speak/read English.

To be eligible to be randomized to receive an intervention (following baseline assessment):

- Type 1 Diabetes Distress Scale (T1DDS) mean score 2.0 or higher;
- HbA1c 7.5 or higher.

Exclusion criteria:

- Documented psychosis, blindness, dementia, active dialysis, substance abuse, amputations, or severe functional deficits, or recent major surgery or hospitalization in the past year.

Consent process

During the telephone screening call, patients will be invited to give verbal consent to be screened for eligibility. Verbal consent will be documented by the researcher. Following determination of eligibility and interest, the study protocol will then be described to individuals. During the initial recruitment conversation, potential participants will be asked open-ended questions and they will be invited to repeat back their understanding of the study. Individuals will then be asked to report their name, mailing address, phone number, and email address.

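### Hypothesis 1 makes three pairwise claims, but Helmert contrasts with no stated arm order leave at least one of them without a pre-specified test

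*Combined protocol and SAP*

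**What the plan says.** Aims & Hypotheses, Primary Specific Aim 1 Hypothesis 1, states that improvement to 12 months in HbA1c, diabetes distress and the secondary outcomes "will be greater in TunedIn relative to StreamLine, and greater in FixIt relative to either TunedIn or StreamLine". That is three ordered pairwise claims for each outcome.

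The Data Analysis section fits an ANCOVA of the follow-up value on baseline and treatment group. The follow-up step is conditional: "When the treatment group effect was statistically significant" (p < 0.05), "Helmert contrasts will be used to determine differences among the three groups". Tests are two-sided at 0.05. The section gives no coefficients, arm order or coding direction, and no pairwise tests.

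Two other places bear on the order, though neither is tied to the contrasts. The Interventions section numbers the arms StreamLine, TunedIn, FixIt. Research Design describes the aim as "to test the added value of a DD-targeted intervention (TunedIn) vs. a unified DD and management intervention (FixIt), relative to a traditional" programme, which casts StreamLine as the reference.

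**The concern.** Three arms have two degrees of freedom between them, so a Helmert set has two contrasts: one arm against the average of the other two, then the remaining pair. The hypothesis has three pairwise claims, and only one of them is a member of the set.

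The risk lies in interpretation. With StreamLine set apart, an effective FixIt alone can make the average of the two newer programmes beat StreamLine, and this could be reported as TunedIn beating StreamLine. With FixIt set apart, a weak StreamLine alone can pull the average down, and this could be reported as FixIt beating TunedIn. In both cases rejecting the averaged contrast is correct; the pairwise reading is not. If the missing pair is added after the data are seen, it is no longer a pre-specified test. The two claims at risk are the trial's added-value questions: whether the distress-targeted programme beats standard management, and whether the unified programme beats the distress-targeted one.

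**Working it through.** **Inputs from the documents.** Two-sided alpha 0.05 and an omnibus test at 0.05 (Data Analysis); d = 0.47, 90 per group, 20% attrition (sample size paragraph); "baseline N=118 per arm" (Research Design).

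**The plan's own figure.** The sample size paragraph says that "a sample of 90 per group allows for detection of moderate effect sizes", d = 0.47, and names no target power. A two-sample t test with 90 per group and d = 0.47 has power 0.88; 80% power needs 72 per group. It is unclear whether 90 is before or after attrition, so I use a range for the analysed number: 90 × 0.8 = 72 at the low end and 118 × 0.8 = 94 at the high end. The finding itself does not depend on this figure.

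**Algebra (no assumption about effects).** Write S, T, F for mean improvement in StreamLine, TunedIn and FixIt.

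- *StreamLine apart:* c1 = (T + F)/2 − S and c2 = F − T. Then F − S = c1 + c2/2, and T − S = c1 − c2/2.
- *FixIt apart:* c1 = F − (T + S)/2 and c2 = T − S. Then F − S = c1 + c2/2, and F − T = c1 − c2/2.
- *TunedIn apart:* c1 = T − (S + F)/2 and c2 = F − S. Only F − S is tested directly, and c1 matches none of the claims.

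In the first two orders a plus sign carries FixIt over StreamLine; a minus sign leaves the third claim open.

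**The same on the t scale (equal arms, StreamLine apart).** Var(c1) = 1.5σ²/n, and any pairwise difference has variance 2σ²/n. The weight on t(c1) is therefore √(1.5/2) = 0.866:

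- t(F − S) = 0.866 t(c1) + 0.5 t(c2)
- t(T − S) = 0.866 t(c1) − 0.5 t(c2)

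With both contrasts just at the critical value 1.97, t(F − S) = 1.706 + 0.985 = 2.69 and t(T − S) = 1.706 − 0.985 = 0.72 (p about 0.47). Two significant contrasts thus secure FixIt over StreamLine and can leave TunedIn over StreamLine with almost no support.

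**Illustration.** 400,000 simulated trials per scenario. Assumed, not from the documents: SD 1, equal variances, independent participants, no gain from the covariate, and the mean patterns shown. All results are after the omnibus gate, in the hypothesised direction, for n = 72 / 90 / 94 per arm.

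| True S, T, F | Arm set apart | Both contrasts favour Hypothesis 1 | Direct test of the pair left out |
|---|---|---|---|
| 0, 0, 0.47 | StreamLine | 29.6 / 39.0 / 41.0% | T > S: 2.5% at each n |
| 0, 0, 0.47 | FixIt | 2.3 / 2.4 / 2.4% | F > T: 76 / 86 / 87% |
| 0, 0.47, 0.47 | FixIt | 29.6 / 39.0 / 40.9% | F > T: 2.5% at each n |
| 0, 0.47, 0.47 | StreamLine | 2.2 / 2.4 / 2.4% | T > S: 76 / 86 / 87% |
| 0, 0.235, 0.47 | either | about 20% (n = 72) to 29% (n = 94) | 28 / 34 / 35% |
| 0, 0.47, 0.94 | either | about 80% (n = 72) to 89% (n = 94) | 80 / 88 / 89% |

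The direct FixIt over StreamLine test was significant in every simulated trial in which both contrasts were, as the algebra requires.

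**The case against.** The strongest reply is that nothing in the plan is invalid. Helmert contrasts are proper tests, the plan never says that two significant contrasts prove Hypothesis 1, and the fitted ANCOVA already contains all three pairwise differences. The arm order can also be guessed: Helmert coding on the numbered list sets StreamLine apart, which fits the reference role it has in Research Design, the moderator hypothesis (FixIt against TunedIn) and the cost-effectiveness hypothesis (both against StreamLine).

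Much of this stands, and it rules out three stronger readings.

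- A reader might infer a false-positive rate of 30% to 41%. The documents do not support that, because they state no rule turning the averaged contrast into a pairwise claim. Nor does it help to say that about 97% of those trials lack a significant direct test: the true difference there is zero, so the directional test fails in 97.5% of all trials.
- A reader might infer that the unstated order decides the result. It changes joint success when two arms are equal, but not when the arms are evenly spaced.
- A reader might infer that the trial cannot answer its question. It can; what is missing is the specification.

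What does not stand is that the likely order resolves the matter. Reverse Helmert coding on the same list sets FixIt apart, and the text names neither form. Even with StreamLine set apart, TunedIn over StreamLine has no planned test.

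**Conclusion.** The concern holds as a gap in pre-specification for the primary hypothesis. By algebra alone, any three-arm Helmert set tests one hypothesised pair directly and covers at most two of the three claims. The claim left out is TunedIn over StreamLine under the order that best fits the rest of the document, or FixIt over TunedIn if FixIt is set apart.

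The scale of possible misreading is illustrative. When only FixIt works, by 0.47 SD, and StreamLine is set apart, both contrasts succeed in about 30% to 41% of trials against 2.5% for the direct test of the missing pair. This rests on the assumed means, SD 1, independent participants and 72 to 94 analysed per arm. It should be corrected before analysis, but the design and the data collection are unaffected.

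**What to change.** Replace the Helmert sentence in the Data Analysis section with:

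> If the omnibus treatment effect is significant at 0.05, the three pairwise differences in adjusted means (TunedIn−StreamLine, FixIt−TunedIn, FixIt−StreamLine) will each be tested at two-sided 0.05 from the same fitted model at each follow-up, with 95% CIs. Hypothesis 1 is judged at 12 months, and superiority over a comparator is claimed only if that pairwise test is significant. Where an ordinal, Poisson or logit model is used, the same three contrasts are taken from that model.

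If Helmert contrasts are kept as an extra analysis, state the arm order.

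With three arms and independent participants, the omnibus gate holds family-wise error at about 5% per outcome and time point (0.049 to 0.050 in simulation). It does not deal with multiplicity across the two primary outcomes. Nor does it deal with clustering from workshop groups of 8 to 10, which would affect Helmert and pairwise tests alike.

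The change costs a few lines of wording and no data or participants. The price is candour about power. For a 0.47 SD pair, gated power is about 76% (72 per arm) to 87% (94 per arm) when the other two arms are equal. All three tests succeed in 61% to 79% of trials if each adjacent gap is 0.47 SD, but in only 3% to 6% if each is 0.235 SD. A Bonferroni split in place of the gate is also valid, with 66% to 79% power for a 0.47 SD pair.
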